## 4.2 Protocol Deviations

In the event the Nu-V3 device is inadvertently removed or the device comes off, the participant will contact the Principal Investigator. The Principal Investigator will determine the appropriate course of action to be taken.

If the study participant is unable to wear the device on their left ear, the study participant will be allowed to wear the device on their right ear, which will result in a minor study deviation. Left-ear deviations could be due to discomfort, sleep position, pain at the local site, or infection. A lack of significant improvement by the end of week 4, per the Principal Investigator's discretion, can also result in a deviation from left-ear placement.

Device placement should be recorded on the study treatment form within the electronic data capture system.

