## 8.0 STUDY ENDPOINT and DATA ANALYSIS

### 8.1 Primary Endpoints: Primary endpoints consisted of the following:

Safety: The primary safety endpoint is the occurrence of reported unanticipated problems involving risk to subjects or others (“UPIRTSOs”). These UPIRTSOs are defined as those problems which alter the risks to subjects or others. This includes any study suspensions or holds. The primary safety endpoint analyses will be based on a risk-benefit conclusion.

Effectiveness: The primary effectiveness endpoints are an overall change in median reported symptoms of pain, anxiety, depression, and/or sleeplessness via numeric rating scales at 8 weeks. This primary effectiveness is measured by median reported symptom changes in pain, anxiety, depression, and/or sleeplessness for respective stratified populations via the following validated tools: Pain - Pain Intensity and Interference (PEG\_Scale), Anxiety - Generalized Anxiety Disorder 7-item (GAD-7) scale, Depression - Patient Health Questionnaire (PHQ-9), Sleeplessness - PROMIS short form 4a, and overall improvement of quality of life (QOL) - Patient’s Global Impression of Change (PGIC).

The hypothesis-driven criterion of effectiveness is to show that there is a statistically significant reduction in the median reported pain, anxiety, depression, and/or sleeplessness levels of patients using the Nu-V3 device. The second criterion is intended to show that there is a statistically significant improvement in reported quality of life and perceived treatment benefit, secondary to overall reported symptom reductions of pain, anxiety, depression, and/or sleeplessness.

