## Appendix 9: Treatment Form

### Weekly Treatment Form

Subject ID \_\_\_\_\_ Date (dd/mmm/yyyy): \_\_\_\_/\_\_\_\_/\_\_\_\_

1. Device Serial Number: \_\_\_\_\_

2. Was the device placed on the participant's left ear?

Yes     No    If no, reason why: \_\_\_\_\_

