**Form PTB-7: Patient's Perceived Treatment Benefit**

[figure not shown]
For *initial assessment* of all symptoms, please rate your average symptom score prior to any treatment (i.e. over the last 30 days)

For any assessment *after treatment has been initiated*, please rate your global average symptom score since your last treatment

1. On a scale of 0-100%, how much benefit do you feel you have received from the Nu-V3 treatment in helping your symptoms?

2. How comfortable was the Nu-V3 device to wear?

3. Have you had any major discomfort from the device that has necessitated you to adjust the device placement?

\_\_\_\_ Yes  
\_\_\_\_ No

[figure not shown]
Subject ID \_\_\_\_\_ Date (dd/mmm/yyyy): \_\_\_\_/\_\_\_\_/\_\_\_\_

For *initial assessment* of all symptoms, please rate your average symptom score prior to any treatment (i.e. over the last 30 days)

[figure not shown]
For any assessment *after treatment has been initiated*, please rate your global average symptom score since your last treatment

4. Please rate your pain, anxiety, depression, and/or sleeplessness on a 0-10 scale:

[figure not shown]
Pain Level:

Anxiety Level:

Depression Level:

Sleeplessness Level:

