Risks to Health: Potential unanticipated problems require prompt reporting to Aspire IRB. These problems potentially place subjects or others at greater risk of physical or psychological harm than was previously recognized, and warrant consideration of substantive changes in the protocol or informed consent process or other action in order to protect the safety, welfare, or rights of participants. Aspire IRB must be notified within 5 calendar days of the event. The completed IRB Unanticipated Problem form (Appendix 3) must be received by Aspire IRB within 10 calendar days of the event. Unanticipated problems are defined as those problems which alter the risks to subjects or others. This includes any study suspensions or holds. This form will be used to report any problem that is unforeseen or involves risk. One form will be used per event or problem.

Table 4.1: Unanticipated Problems Involving Risk to Patients or Others			
	Phase I	Phase II	Total
UPIRTSO 1 (number)			
UPIRTSO 2 (number)			
UPIRTSO 3 (number)			
Overall UPIRTSOs Reported			

Table 4.2: Risk/ Mitigation Measures	
Identified Risk	Mitigation Measures

Insert Safety Analysis Here

Section 5.0: Results

Results: The principal safety and effectiveness results from patients in the Nu-V3 study are provided below. The primary safety analysis was based on all patients registered and included all reported UPIRTSO events. The primary safety endpoint included imputation for missing clinical outcomes data using the logistic regression method. The imputation model included baseline characteristics including age, sex/gender, marital status, primary language spoken, race/ethnicity, education history, and veteran status.

Primary Safety Endpoint:

Insert Primary Safety Endpoint Statistical Analysis

Insert Primary Safety Endpoint Statistical Table

Primary Effectiveness Endpoint:

Insert Primary Effectiveness Endpoint Statistical Analysis

Insert Primary Effectiveness Endpoint Statistical Table- 8 weeks

Secondary Effectiveness Endpoint:

Insert Primary Effectiveness Endpoint Statistical Analysis

Insert Primary Effectiveness Endpoint Statistical Table: 4, 8, 12 weeks

Sub-Analyses:

Insert Sub-Analyses Statistical Analysis

Insert Sub-Analyses Statistical Tables

Special Controls:

Insert Special Control Section Here

Benefit/Risk Determination:

Insert Benefit/Risk Section Here

Section 5.0: Administrative Information

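### The primary safety result counts only UPIRTSOs, and two unreconciled wordings leave open whether non-serious local harms are counted at all

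*Protocol*

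**What the plan says.** Protocol Section 8.1 sets the endpoint: "The primary safety endpoint is the occurrence of reported unanticipated problems involving risk to subjects or others". It then defines the term: "These UPIRTSOs are defined as those problems which alter the risks to subjects or others", with study suspensions and holds included. The analysis rule is one sentence: "The primary safety endpoint analyses will be based on a risk-benefit conclusion". No rate, threshold or interval is given. The SAP repeats the definition under Primary Endpoints, and its Section 5.0 (Results) states: "The primary safety analysis was based on all patients registered and included all reported UPIRTSO events". SAP Table 4.1 has UPIRTSO rows and a UPIRTSO total, and no row for any other event.

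Protocol Section 7.0 and SAP Section 4.0 (Risks to Health) give the same definition. Both then say that the Unanticipated Problem Form is for any problem that either was not foreseen or carries risk, with one form per event. The form (Protocol Appendix 7) records CTCAE grade 1 to 5 and relationship to the device. It also asks for an SAE term and serious criteria.

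On moving the device, Protocol Section 4.2 says "the study participant will be allowed to wear the device on their right ear, which will result in a minor study deviation" and gives reasons: "Left-ear deviations could be due to discomfort, sleep position, pain at the local site, or infection". The weekly Treatment Form (Appendix 9) asks "Was the device placed on the participant's left ear" and leaves a free-text line for the reason if not. Item 3 of Form PTB-7 (Appendix 11) asks "Have you had any major discomfort from the device that has necessitated you to adjust the device placement", answered yes or no.

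**The concern.** The device is worn on the ear 24 hours a day during an 8-week treatment period, so local reactions are an obvious kind of harm to look for. The plan has no general adverse-event endpoint or adverse-event table, and the assessment tables in Protocol Section 4.1 list no adverse-event form. The one safety count is tied to a definition that a mild local reaction, of a kind the protocol already mentions, need not meet. The SAP presents this as the pivotal study behind a De Novo request, and safety is to be judged by weighing risk against benefit. If the risk side holds only UPIRTSOs, a reader could take a zero as evidence of local tolerability that the analysis never measured.

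**Working it through.** The documents state no safety rate, power or precision figure, so there is nothing to reproduce. The check follows a non-serious local problem through the plan, then looks at what a zero count would show.

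**Step 1: where a non-serious local problem goes.**

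| Route | What is recorded | Planned use |
|---|---|---|
| Site follows the endpoint definition (Protocol 8.1; SAP Primary Endpoints) | Nothing, if the problem is judged not to change the risks | None |
| Site follows the wider form wording (Protocol 7.0; SAP 4.0) | Unanticipated Problem Form with grade and relatedness | Enters Table 4.1 only if it is then counted as a UPIRTSO; no other row exists |
| Problem leads to an ear switch (Protocol 4.2) | Minor deviation for the switch; reason as free text on the Treatment Form | No safety use stated |
| Patient answers yes to PTB-7 item 3 | Yes/no, without cause or grade | PTB-7 is an effectiveness tool in Protocol 8.2, and comfort is a sub-analysis in 8.3; no safety use |
| Check of device effects at each session (Protocol 4.0) | No form named | None stated |
| SAE leading to exit (SAP Tables 1 and 2) | Exit reason | Disposition only; not relevant to a non-serious event |

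Only the second route can reach the primary safety result, and it depends on the site's reading. A local reaction with no ear switch has no dedicated safety record unless the site files the form.

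**Step 2: what zero UPIRTSOs would show.** Input: n = 50 to 100 (Protocol Section 4.0). With zero events, the exact one-sided 95% upper bound is 1 − 0.05^(1/n).

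- n = 50: 1 − 0.05^(1/50) = 0.058, or 5.8%.
- n = 100: 1 − 0.05^(1/100) = 0.0295, or 3.0%.

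The two-sided versions, 1 − 0.025^(1/n), are 7.1% and 3.6%. All four bound the rate of reported UPIRTSOs. None bounds the rate of local pain, discomfort or infection.

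**Step 3: illustration only.** The documents give no rate for local reactions, so p is assumed over a wide range. Expected number affected = n × p; chance of at least one = 1 − (1 − p)^n.

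| Assumed p | n = 50: expected, P(≥1) | n = 100: expected, P(≥1) |
|---|---|---|
| 2% | 1, 0.64 | 2, 0.87 |
| 5% | 2.5, 0.92 | 5, 0.99 |
| 10% | 5, 0.99 | 10, >0.999 |
| 20% | 10, >0.999 | 20, >0.999 |

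In every row the UPIRTSO count from these reactions could be anything from zero to the full number, according to the wording followed.

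**The case against.** The strongest reply is that capture is wider than the endpoint sentence suggests. Both documents extend the form to any problem carrying risk, and the form has a mild grade and a relatedness field. On that wording a local infection is reportable even if foreseen. This stands: exclusion is possible but not demonstrated. It does not close the gap, because the endpoint and Table 4.1 keep the narrower definition, and the form's SAE labels may lead a site to reserve it for serious events.

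Three stronger readings are tempting and are not supported.

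- A reader might infer that Section 4.2 files harms as deviations instead of safety events. The minor deviation is the change of ear, and nothing there prevents the harm from also being reported under Section 7.0.
- A reader might infer that these are acknowledged device effects. The protocol does not call them expected or device-caused. Sleep position is in the same list, and an ear infection could be intercurrent. The consent pages, where anticipated risks might be listed, were not available.
- A reader might infer that the harms can never reach a safety analysis. The SAP's safety analysis, risk/mitigation table and benefit/risk section are unfilled placeholders. They prespecify nothing, but they do not rule it out.

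**Conclusion.** The point holds as one of incomplete and inconsistent definition. Followed as written, the plan could yield a primary safety result of zero, and a risk-benefit conclusion resting on it, while non-serious local pain, discomfort or infection had occurred. Zero here means zero in the primary endpoint and Table 4.1; SAE exits and comfort scores could still appear elsewhere. How many harms would be missed cannot be stated, since it depends on an unknown rate and on each site's reading. The assumed rates above show only that, at this sample size, even uncommon reactions would probably occur at least once. It would go too far to call the endpoint biased: it measures what it defines, but that is too narrow to support a statement about local tolerability.

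**What to change.** 1. Reconcile Protocol Section 7.0 with Section 8.1, and the matching SAP text. Any problem involving risk, foreseen or not, should be reported on the existing form with its CTCAE grade and device relatedness, and the form's SAE labels should plainly admit non-serious events. In SAP Table 4.1, give the number and percentage of registered patients with any such event and with any device-related event, each with an exact 95% interval, and show UPIRTSOs as a subset.
2. Add separate descriptive safety rows for ear switches because of pain, discomfort or infection (from the Treatment Form) and for a positive answer to PTB-7 item 3. Do not class these automatically as device-related adverse events, because neither source records cause or grade.

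The second change uses data already collected, apart from coding the free-text reasons. The first does not: grade and relatedness are only on the Unanticipated Problem Form, so sites would complete it somewhat more often. The form also carries IRB deadlines of 5 and 10 calendar days, so the amendment should say how these apply to the added events. The other downside is a less favourable-looking safety count.

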### 3.2 Exclusion Criteria

- Participants with a Pacemaker
- Participants with irregular heart rate or a heart rate lower than 60 beats per minute (bradycardia)
- Have had a transplant within the last 2 years
- Have had a heart attack or cardiac bypass surgery within the last 12 months
- History of substance abuse, including prescription drugs, within the last 12 months
- Patients with complaints of dizziness or lightheadedness within the last 3 months
- Women who are pregnant

- Participants with Diabetic Retinopathy
- Current Ear infection
- SBP < 100 and/or DBP < 60
- History of uncontrolled bipolar disorder within the last 12 months
- History of uncontrolled seizures within the last 12 months
- History of Aneurysms
- History of syncope within the last 12 months
- Participants that have had a TIA or stroke within the last 12 months
- Participants with health problems deemed at risk for the study by the Principal Investigator
- Participants with any changes to Pain/Anxiety/Depression/Sleeplessness medications within last 60 days (participants that do not meet this medication-change washout period may be delayed until 60-day period is met)
- Participants that are currently under adjudication process for disability support, VA or other

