**Use and Care Instructions**

Once the device and all pads have been placed, instruct the patient on the use and care of the device for the time he or she will be wearing it and be sure they have the instructions to take with them.

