**Nu-Life Products, Inc**

Manufacturing and Supply of Nu-7

**Important:** Before applying the device, read all use and safety instructions on the reverse side.

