### SAFETY INSTRUCTIONS

These safety instructions are an integral part of the Nu-V3 and the therapy provided by the device and as such, must be followed closely to ensure the proper use of the device and safety of the treatment. These instructions for use and safety instructions are to be read and observed in full by every user. Treatment Provider and patient are both responsible for educating themselves and following these instructions and the proper use of the device as described in these instructions. Non-observance of the warnings and safety instructions may lead to injuries, infections or serious harm to the user and others.

The exclusive PADS™ assembly is only intended for single use. The re-use of single-use products represents a possible risk for the patient or user. Never place the exclusive gel pads on any location other than the auricular (ear) area, especially the eyes. It is important that all used devices and PADS™ assemblies are not reused in any way and that the device and PADS™ assembly is removed by the treatment provider or returned to the treatment provider by the patient or user.

Use of the device in the immediate vicinity of short-wave, or RF devices can be a cause of interference and should be avoided. The serial number for the Nu-V3 device is located on the packing for each device. These serial numbers are kept on file with the manufacturer and should be kept by the treatment provider and filed with the patient's reports on a regular basis.

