### Absolute Contraindications

- History of dizziness or lightheadedness within the last 30 days
- Current ear infection
- Heart rate lower than 60 beats per minute (bradycardia)
- SBP < 100 and/or DBP < 60
- Heart attack within the last 12 months
- Cardiac bypass surgery within the last 12 months
- History of uncontrolled seizures
- Aneurysms
- History of an organ transplant within the last 2 years
- Pregnancy
- Diabetic Retinopathy
- Uncontrolled Bipolar Disorder within last 12 months

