### Relative Contraindications

- The following should be discussed with the patient's physician before use.
- Patients with a pacemaker
- History of syncope within the last 12 months
- History of TIA or stroke within the last 12 months
- Need for obtaining an MRI during the time the device is in place

Because the gel pads are non-invasive and use a specialized electro-gel to transmit the stimulation signal from the device to the nerves, the patient may or may not feel a gentle pulsing. This pulsing may diminish or stop as the body gets used to the stimulation. This is normal and is not an indication that the device is not working. The device is water resistant but not waterproof. When showering, patient should use the clear ear covers supplied with the device to ensure that the device stays dry. Do not allow the device to come in direct contact with water. Direct contact with water may result in the malfunction of the device.

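### Section 4.2 allows a right-ear switch for an undefined infection as a minor deviation, with no pause or review, although binding device instructions make current ear infection an absolute contraindication

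*Protocol*

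**What the plan says.** Protocol section 4.2 (Protocol Deviations) deals with a participant who cannot wear the device on the left ear: "the study participant will be allowed to wear the device on their right ear, which will result in a minor study deviation". It then gives examples of the cause: "Left-ear deviations could be due to discomfort, sleep position, pain at the local site, or infection". The section does not say what kind of infection is meant or where. It asks for device placement to be recorded on the treatment form.

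Appendix 6 (Use and Care Instructions) lists "Current ear infection" under Absolute Contraindications, with no side and no exception. The separate list of Relative Contraindications, headed "The following should be discussed with the patient's physician before use", does not include it. The Safety Instructions in Appendix 6 describe themselves as part of the device and its therapy and call for close adherence. They also say "Treatment Provider and patient are both responsible for educating themselves and following these instructions".

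The entry criterion in section 3.2 is "Current Ear infection", again with no side. The eligibility checklist in Appendix 4 and the SAP's key exclusion criteria repeat it.

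**The concern.** Section 4.2 gives a site an express permission, and infection is one of its named triggers. A site that uses the permission when a participant develops an ear infection would keep that participant on a device worn 24 hours a day, in a state that the device's own instructions treat as an absolute bar. Calling the switch a minor deviation groups infection with sleep position and discomfort. It may also lead a site to log the event as a deviation and go no further. In a multi-center study, one site could move the device to the other ear while another takes it off. What is at stake is participant safety and consistent handling across sites.

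**Working it through.** The documents give no figure on this point, so the check sets the texts side by side.

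1. **What section 4.2 permits.** Right-ear wear, classed as a minor deviation. It allows the switch and does not order it.

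2. **What section 4.2 attaches to infection.** Nothing further. The section brings in the investigator twice: to decide the course of action when the device comes off, and to use discretion when there is no significant improvement by the end of week 4. Neither provision covers infection.

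3. **What Appendix 6 rules out.** Current ear infection, absolutely and with no side named. Moving the device from an infected left ear to the right ear does not take the participant outside that wording.

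4. **Whether Appendix 6 applies during wear.** It does. Appendix 5 tells the provider to "instruct the patient on the use and care of the device for the time he or she will be wearing it" and to see that the patient takes the instructions away. It also says "Before applying the device, read all use and safety instructions on the reverse side", and an ear switch is a fresh application. The exclusion in section 3.2 is weaker support, because the section 4.1 schedule checks inclusion and exclusion only in week 1. The conflict therefore rests on Appendix 6.

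5. **The two readings of infection.**
   - *An ear infection:* section 4.2 permits wear that Appendix 6 rules out.
   - *A skin infection at a pad site only:* neither section 4.2 nor Appendix 6 says whether the contraindication covers it.

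6. **Whether other provisions close the gap.**
   - Sessions include a check for device effects (section 4.0). This could reveal an infection but does not say what to do about it.
   - The weekly treatment form (Appendix 9) asks for a reason if the left ear was not used. It prompts no action.
   - Section 7.0 reporting may apply, but it holds no rule for stopping the device.
   - The SAP's Accountability section lets a physician end participation. That is an exit, not a pause.

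7. **Opportunity to act.** From the section 4.1 schedule, weeks 1 to 8 have 8 in-office assessments. A new device is placed in weeks 1, 3, 5 and 7 (4 visits) and pads are replaced in weeks 2, 4, 6 and 8 (4 visits); 4 + 4 = 8. The device or pads are therefore handled at every treatment-week visit, and 8 − 1 = 7 of those visits follow the first application. This counts existing contact. It does not measure risk.

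**The case against.** The strongest reply is that the conflict needs an equation the text never makes. Section 4.2 says *infection*, not *ear infection*, straight after mentioning pain at the local site, and the device works through three surface gel pads. A pad-site skin infection is a natural reading, and moving to the unaffected ear may then breach nothing. This stands as a limit: on that reading the defect is an undefined term, not a contradiction.

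Second, section 4.2 classifies deviations. It gives examples, permits without ordering, and contains nothing that overrides a contraindication. A site could satisfy both texts by holding the device until the infection clears. That is right, but section 4.2 does not say so, and a protocol should not permit without condition what its device instructions forbid.

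Third, a reader might infer that nothing tells a site which text prevails. The documents do not support that. Appendix 6 demands adherence, so where the contraindication applies, the device instructions already say not to use the device. The defect is that section 4.2 grants a permission at odds with a governing instruction.

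Fourth, the device is non-invasive, is described as nonsignificant risk per IRB review, and would be moved away from an infected left ear. This tempers the likely harm, but the contraindication is absolute and does not turn on which ear is affected.

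Finally, the consent pages were removed and the process maps in Appendix 3 are not readable. Handling rules could be stated there, so the absence is asserted for the readable text only.

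**Conclusion.** The point holds in a limited form. Where the infection is an ear infection, the section 4.2 permission, used as written, allows wear that the binding device instructions rule out. Where it is only a pad-site skin infection, the documents leave open whether the contraindication applies.

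A reader might go further and infer that the protocol directs infected participants to keep wearing the device, or that treatment results are compromised. Neither follows: section 4.2 permits and does not direct, and nothing in the documents shows an effect on an endpoint or conclusion. No exposure figure can be given, since neither the frequency nor the duration of ear infection can be derived.

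The correction should be made, for participant safety and for consistent handling across sites. Confidence is medium, because the meaning of *infection* is unsettled and part of the protocol could not be read.

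**What to change.** Remove infection from the section 4.2 examples of minor ear-side deviations. Add a rule: if an ear infection develops, the device is interrupted on both ears until the infection has cleared and the investigator has reviewed the participant; the event is assessed under section 7.0; questionnaires continue.

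If the sponsor and IRB intend a pad-site skin infection, or an infection of one ear only, to fall outside the contraindication, state that exception in the same words in section 4.2, Appendix 6 and the exclusion criteria (section 3.2, the Appendix 4 checklist and the SAP summary). Require investigator review before any switch.

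This is a wording amendment. The Appendix 7 form already offers interruption as an action taken and asks about recurrence after restart. The check fits the 8 existing treatment-week visits, and questionnaires already run with the device off in weeks 9 to 12. No new visits, staff or tests are needed. The downside is some lost treatment days within the 8-week treatment period for affected participants; their number cannot be derived from the documents.
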